10.0 Study Endpoints

10.1 Primary Endpoint

The primary endpoint is a composite endpoint represented by the occurrence of any major thromboembolic event (stroke [i.e., ischemic, hemorrhagic or cryptogenic] that is an acute onset of a focal neurologic deficit of presumed vascular origin lasting for ≥ 24 hours or resulting in death) or major hemorrhagic complication (major bleeding) during the 12-month Evaluation Period.

10.2 Secondary Endpoints

The secondary endpoints supporting the study objective are:

Safety Endpoints:

- Minor bleeds
- Hospitalization with any thromboembolic or major hemorrhagic event
- All cause mortality

Additional Endpoints:

- QoL (SF-36)
- AF recurrence
- Repeat ablation for AF

11.0 Treatment Description

11.1 Prior Ablation Procedure

Subjects enrolled in the OAT Pilot Study have previously undergone successful cardiac ablation in accordance with institutional standards of care (SOC). SOC is the clinical work flow and process that physicians follow in their practice when using commercially available devices (without any mandated protocol requirements) as required by the investigator's institution.

11.2 Medication Management

11.2.1 OAT Management

Prior to enrollment in the OAT Pilot Study, subjects' OAT should be administered at the discretion of the investigator and in accordance with current AF management guidelines.^{6, 30-32} Subjects should continue their physician-prescribed regimen for OAT until they are enrolled in the OAT Pilot Study. Subjects randomized to the OAT (Control) Group should continue their current OAT regimen; however, changes are allowed per the investigator's discretion (i.e., from one type of OAT to another) during the Evaluation Period. All commercially approved OAT medications may be prescribed to subjects in the OAT (Control) Group. Subjects in the OAT Withdrawal (Test) Group who resume OAT during the Evaluation Period, regardless of the reason, will be discontinued from the study at the time when OAT therapy is resumed.

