Although the efficacy of warfarin in preventing stroke in AF patients has been clearly demonstrated, oral anticoagulation is still underused in clinical practice for several reasons. Firstly, oral anticoagulation therapy carries a substantial risk of hemorrhage; this could be underestimated in clinical practice, considering the restrictive selection criteria used in randomized trials, in which patients with lower risk of bleeding are often enrolled. For example, in the SPINAF trial only 7% of the 7982 patients initially screened were enrolled.¹⁰ Moreover, the risk of hemorrhage is strictly related to the patient's age. Indeed, the incidence rate of major hemorrhage has been found to rise from 1.5 per 100 patient-years for patients younger than 60 years to 4.2 per 100 patients-years for patients older than 80 years (hazard ratio of 2.7).¹¹ In a meta-analysis of major randomized trials of oral anticoagulation therapy, the mean age of patients was 69 years, and only 20% of participants were older than 75 years.⁹

By contrast, in clinical practice this latter group of patients represents more than 50% of the population that needs to be treated with anticoagulation therapy.⁷ The second reason for the underuse of oral anticoagulation is that this therapy, specifically warfarin, is associated with restrictions in everyday life, as it requires frequent monitoring of the INR level in order to adjust the therapeutic dosage. Finally, it is well known that a considerable percentage of patients are unable to comply with oral anticoagulation therapy. In warfarin-treated patients, discontinuation of this therapy occurs at rates of up to 38% a year and approximately 50% of strokes occur during inadvertent therapeutic lapses or in subjects who temporarily or permanently cease therapy.⁸

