9.7 Subject Withdrawal

The investigator may remove a subject from the study for any of the following reasons: withdrawal is in the subject's best interest, subject preference, concurrent illness, noncompliance, or any other situation the investigator deems a compromise to the integrity of the study. Subjects will be informed prior to study entry that they are free to withdraw from the study at any time and for any reason, without prejudice to his or her future medical care by the physician or the institution.

If a subject is removed from the study, the date and reason for withdrawal will be recorded on the appropriate electronic case report form (eCRF). If the subject is withdrawn due to an adverse event (AE) or serious adverse event (SAE), the Investigator must comply with all reporting requirements described in Section 12 and must follow the subject until the AE/SAE has resolved or stabilized.

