11.3 Management of Arrhythmia Recurrence

If there is AF recurrence after the subject is randomized to one of the study arms, the subject should be treated according to institutional Standards of Care (SOC), which is defined as the clinical work flow that physicians follow in their practice (without any mandated protocol requirements) and the processes required by the investigator's institution. Subjects who experience an AF recurrence and/or undergo a repeat ablation or resume OAT (for subjects in the OAT Withdrawal [Test] Group) for AF will be discontinued from the study.

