13.0 Statistical Analysis Plan

13.1 Study Objective

The objective of this study is to assess whether the patients who discontinued OAT after a successful AF ablation are not inferior to the group of patients who continued OAT after a successful AF ablation in terms of the composite endpoint of all ischemic and hemorrhagic events.

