13.4 Analysis Population

The study contains two treatment arms with subjects either discontinuing OAT or continuing OAT. The primary analysis will be based on the intent-to-treat principle where subjects will be analyzed by the group to which they are randomized, regardless of actual treatment received. Lost-to-follow-up, discontinued, and withdrawn / early termination subjects will also be included in this analysis.

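### OAT crossover ends follow-up in the test arm but has no rule in the control arm, so the stated intent-to-treat comparison cannot be carried out as written

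*Combined protocol and SAP*

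**What the plan says.** **Test arm.** Section 11.2.1 makes exit mandatory: "Subjects in the OAT Withdrawal (Test) Group who resume OAT during the Evaluation Period, regardless of the reason, will be discontinued from the study". Section 11.3 has a second test-only rule, tied to AF: subjects who "resume OAT (for subjects in the OAT Withdrawal [Test] Group) for AF will be discontinued from the study". Section 13.7.1 censors discontinued subjects who have not had a primary event at their last visit.

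**Control arm.** Section 11.2.1 asks these subjects to stay on OAT and provides only for a switch of agent: "changes are allowed per the investigator's discretion (i.e., from one type of OAT to another) during the Evaluation Period". Stopping OAT is not mentioned. Under its Discontinued category, 9.6 lists only arrhythmia recurrence, which applies to both arms. Section 9.7 lets the investigator remove a subject for reasons that include "subject preference, concurrent illness, noncompliance, or any other situation the investigator deems a compromise to the integrity of the study", but does not require it.

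**Analysis.** Section 13.4 names one population, under which "subjects will be analyzed by the group to which they are randomized, regardless of actual treatment received". Section 13.1 asks whether patients who discontinued OAT "are not inferior to the group of patients who continued OAT after a successful AF ablation". No on-treatment analysis and no summary of time off the assigned strategy is planned. Section 13.3 states that the pilot is not powered for inference.

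**The concern.** An intent-to-treat comparison needs outcomes after crossover in both arms. Here a test subject's data end at or before OAT is resumed, while a control subject's data continue, by default, after OAT is stopped. The two arms follow different principles under one label.

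Two distortions can result.

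- **Test arm: informative censoring.** Resumption may be related to risk. For example, a focal deficit that lasts less than 24 hours is not a stroke under 10.1. If it leads to resumption, the subject leaves and a later stroke is never counted. Scheduled visits fall at 3, 6 and 12 months, so censoring at the last scheduled visit could precede a late resumption by nearly 6 months.
- **Control arm: dilution.** Time off OAT is counted as OAT continuation and makes the arms look more alike. Stopping is plausible: the trial is unblinded, and 5.1 says of warfarin that "discontinuation of this therapy occurs at rates of up to 38% a year".

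In a study whose objective is worded as non-inferiority, a reader would take similar event rates as reassurance. Nothing planned would show how much of the similarity came from crossover.

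**Working it through.** **1. The plan's own figure.** The only design figure is 100 subjects, 50:50 (13.3). It has no stated derivation and no allowance for crossover, so there is nothing to reproduce.

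**2. The rules side by side.**

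| | Test subject resumes OAT | Control subject stops OAT |
|---|---|---|
| Rule | Mandatory exit (11.2.1; 11.3 if for AF) | None |
| Follow-up | Ends | Continues by default; investigator may withdraw (9.7) |
| Primary analysis | Censored at last visit (13.7.1) | Analysed as randomized (13.4) |

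The size of the test-arm effect cannot be calculated, because the documents give no resumption rate. Only the control-arm dilution can be illustrated.

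**3. Inputs, all from 5.1, used as assumptions.** Warfarin in general AF: 62% relative stroke reduction; absolute reduction of 2.7 points a year (primary prevention) or 8.4 (secondary prevention); 1.2 points a year more major bleeding. Warfarin stopping: up to 38% a year. None is a design input of this trial or a post-ablation figure.

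**4. Difference before dilution.**
- Stroke off OAT = 2.7/0.62 = 4.35% a year, on OAT 4.35 − 2.7 = 1.65%. Secondary prevention: 8.4/0.62 = 13.55%, on OAT 5.15%.
- Net composite difference (off minus on), stroke less bleeding: 2.7 − 1.2 = 1.50 points; 8.4 − 1.2 = 7.20 points.

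**5. Control person-time off OAT.** If a proportion p stops within a year at constant hazard λ = −ln(1 − p), the off-OAT share is f = 1 − p/λ. For p = 0.38, λ = 0.478 and f = 1 − 0.38/0.478 = 0.205. If all stopping happened on day 1, f = 0.38.

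**6. Difference after dilution.** The control rate is (1 − f) × on-rate + f × off-rate, so the difference is multiplied by (1 − f).

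| Stopping per year | f | Primary: points (events per 50) | Secondary: points (events per 50) |
|---|---|---|---|
| 0 | 0 | 1.50 (0.75) | 7.20 (3.60) |
| 10%, gradual | 0.051 | 1.42 (0.71) | 6.83 (3.42) |
| 20%, gradual | 0.104 | 1.34 (0.67) | 6.45 (3.23) |
| 38%, gradual | 0.205 | 1.19 (0.60) | 5.72 (2.86) |
| 38%, day 1 | 0.380 | 0.93 (0.47) | 4.46 (2.23) |

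At 38% with gradual stopping the loss is 0.75 − 0.60 = 0.15 or 3.60 − 2.86 = 0.74 events per 50 subjects. At 10% to 20% stopping the shrinkage is 5% to 10%.

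**7. Direction.** The composite is worse off OAT only if 0.62 × (off-OAT stroke rate) exceeds 1.2, that is, if the off-OAT stroke rate exceeds 1.2/0.62 = 1.9% a year. Section 5.1 gives untreated rates from below 2 to above 10 per 100 patient-years, and 5.2 reports very few thrombotic events after successful ablation on or off OAT. The break-even point is therefore within the plausible range.

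**The case against.** The strongest reply has four parts.

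- **Keeping control stoppers is ordinary intent-to-treat.** This stands. The departure from that principle is on the test side, where subjects who resume "will be discontinued from the study at the time when OAT therapy is resumed". The control side lacks a stated rule and a planned display of the dilution.
- **The documents never say that control stoppers stay.** This also stands. It follows from silence together with 13.4, and 9.7 allows withdrawal for noncompliance, so handling may vary among up to 10 sites. That leaves the rule unspecified in one arm and mandatory in the other, which is still asymmetric.
- **Dilution is small and may be smaller than shown.** The 38% is an upper figure for warfarin. This trial admits other agents, requires two months of prior OAT and willingness to comply, and excludes contraindications to anticoagulation. Stopping after a primary-endpoint bleed does not dilute a time-to-first-event analysis. All fair; the table should be read as an upper range.
- **No inference depends on it.** There is no margin, the log-rank and Fisher tests are tests of equality, and 13.3 disclaims inference. This limits the consequence but does not remove it, because 13.1 still words the question as non-inferiority.

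A reader might infer that the plan is biased in favour of withdrawal, or that a non-inferiority conclusion would be false. The documents support neither. The direction depends on stroke outweighing bleeding, and the plan defines no formal non-inferiority conclusion. The stroke-only contrast (2.70 falling to 2.15 points at 38% stopping) also overstates the effect, since the endpoint includes bleeding, which moves the other way.

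**Conclusion.** The point holds as an asymmetry that the plan should resolve. As written, test-arm follow-up ends at crossover and control-arm follow-up by default does not, so the analysis promised in 13.4 cannot be delivered for test subjects who resume OAT. Their censoring may be informative, to a degree that cannot be quantified from the documents.

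Control-arm dilution is modest: at most about a fifth of the net difference with gradual stopping at the upper 38% figure, or 38% of it if all stopping came on day 1. The day-1 case is about 0.28 to 1.37 events per 50 subjects (0.75 × 0.38; 3.60 × 0.38). These sizes rest on general-AF warfarin rates, additive stroke and bleeding rates, and full 12-month follow-up.

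What is at stake is how the pilot's rates are read and reused in a later trial. It is worth correcting because the correction is cheap.

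**What to change.** 1. **Follow-up (9.6, 9.7, 11.2.1, 11.3).** State that a change in OAT status in either arm is recorded with its date and does not by itself end study follow-up, so that all randomized subjects are followed for the primary endpoint to 12 months. This concerns data collection, not treatment. AF recurrence is a separate exit in both arms under 9.6 and 11.3, and the same wording needs to say whether endpoint follow-up continues after it; without that, intent-to-treat follow-up stays incomplete. Reconcile 11.2.1 (resumption for any reason) with 11.3 (resumption for AF).
2. **Analysis (13.4, 13.7.1).** Keep the intent-to-treat analysis as primary. Add a supportive on-treatment analysis that censors both arms at departure from the assigned strategy (OAT stop date in control, OAT resumption date in test), with one stated rule for events near the switch date.
3. **Display.** Report person-time off the assigned strategy by arm.

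The two analyses need not be required to agree before any statement about non-inferiority, since the pilot has no margin on which to base one.

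**Cost.** An amendment to the follow-up wording, retained follow-up at visits already scheduled, and one extra analysis. Anticoagulation use is already recorded at every follow-up visit (Table 3), medication changes go into the eCRF (11.4.2), and start and stop dates are required in source documents (14.7.3). Continued follow-up adds some dilution from test subjects who resume and leaves the control dilution in the primary analysis; items 2 and 3 make both visible. The on-treatment analysis may itself be subject to selection and is supportive only.

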11.2.2 AAD Management

AADs are defined as class I or class III. Subjects on a stable AAD regimen are allowed to remain on their current AAD regimen. Subjects' AAD regimen should remain constant over the course of the study.

11.2.3 Use of Additional Medications

The use of additional medications during the study will be at the discretion of the investigator for clinical indications.

11.3 Management of Arrhythmia Recurrence

If there is AF recurrence after the subject is randomized to one of the study arms, the subject should be treated according to institutional Standards of Care (SOC), which is defined as the clinical work flow that physicians follow in their practice (without any mandated protocol requirements) and the processes required by the investigator's institution. Subjects who experience an AF recurrence and/or undergo a repeat ablation or resume OAT (for subjects in the OAT Withdrawal [Test] Group) for AF will be discontinued from the study.

11.4 Schedule of Examinations

11.4.1 Study Visits

Table 3 displays the required schedule for subject treatments and evaluations for the test and control groups. Sites participating in this study have been selected on the basis of their capabilities to successfully carry out these assessments.

Table 3. Summary of Subject Assessments

Assessments	Enrollment	Randomization	Evaluation Period			Unscheduled Visit
	Screening/Enrollment (within 30 days prior to randomization)	Baseline/ Randomization	3-Month Follow up Visit (+/- 2 week)	6-Month Follow up Visit (+/- 2 weeks)	12-Month Follow up Visit (+/- 4 weeks)	
Informed Consent Form	✓					
Inclusion/Exclusion Review	✓	✓				
Clinic Visit	✓	✓	✓	✓	✓	✓
Demographics	✓					
Medical History	✓		✓	✓	✓	✓
12 lead ECG		✓	✓	✓	✓	✓
CT/MRI Scan ¹			✓ ¹	✓ ¹	✓ ¹	✓ ¹
Pregnancy Test		✓ ²				
AF Monitoring	✓ ^{3,4}		✓ ⁴	✓ ⁴	✓ ⁴	
Blood Draw ⁵ • INR		✓	✓	✓	✓	✓
QoL		✓ ⁶	✓		✓	
Medication: • Concomitant Medications		✓	✓	✓	✓	✓
• Anticoagulation		✓	✓	✓	✓	✓
• AAD		✓	✓	✓	✓	✓
Adverse Events	✓ ⁷	✓	✓	✓	✓	✓

1. A CT/MRI Scan should be performed to exclude PV stenosis for subjects who are symptomatic.

2. In pre-menopausal women only, if the subject may be pregnant according to menstrual period history. Test must be performed within 72 hours of pre-randomization.

3. A 7-Day Holter Monitor is required at screening during the pre-randomization AF monitoring. Subjects with an ICD or pacemaker may use interrogations for the duration 7 days and within 30 days prior to randomization.

4. Refer to the AF Monitoring description (Section 11.4.2, Subject Assessment Details) for additional information regarding when subjects are required to monitor their heart rhythm for each visit.

5. Only applicable for subjects randomized to the OAT arm.

6. Prior to randomization

7. Once a subject has signed the ICF, all adverse events associated with study required assessments must be collected.

11.4.2 Subject Assessment Details

12-lead Electrocardiogram (ECG)

Data from 12-lead ECG recordings will be collected as described in Table 3. Data from unscheduled ECG's between two consecutive follow-up visits will be collected at the next scheduled visit. A copy of the ECG should be filed in the subject's medical chart with the participating investigator.

Cardiac Computed Tomography (CT) / Magnetic Resonance Imaging (MRI)

A cardiac multi slice CT or MRI should be performed on symptomatic subjects to exclude PV stenosis.

AF Monitoring: Holter Monitor (7-day)

All subjects who have signed the study ICF are required to undergo AF monitoring prior to randomization. The pre-randomization AF monitoring will be conducted by Holter Monitor.

- **Screening/Enrollment:** Subjects will be provided with a 7-day Holter Monitor to confirm that they are free from AF recurrence prior to randomization into one of the study arms. At the end of the Holter Monitoring period, subjects are to send their Holter Monitor to the core lab for analysis.
 - (Subjects are permitted to remove their Holter Monitor during certain activities of daily living during which wearing the device would not be recommended or is impractical (e.g., bathing). However, subjects must be encouraged to be as compliant as possible with Holter Monitoring so that heart rhythm status data can be captured consistently and completely.)
- **Follow-up Visits:** Subjects who are randomized to the off-OAT cohort, it is strongly recommended that some type of continuous monitoring should be performed to screen for asymptomatic AF at regular intervals as noted in the 2012 HRS Expert Consensus Statement³³. At minimum, AF monitoring duration should be for no less than 48 hours and no less frequent than every 6 months. The outcome of the AF monitoring must be clearly documented in the source document and eCRFs. If there is a recurrence of AF, the subject should be treated as described in Section 11.3 – Management of Arrhythmia Recurrence.

For subjects with an implantable cardioverter defibrillator (ICD) or artificial cardiac pacemaker, interrogations for the duration of and within the windows for AF monitoring will be accepted.

Pregnancy Test

A urine sample pregnancy test must be obtained within 72 hours prior to randomization in pre-menopausal women only, if the subject may be pregnant by the history of their menstrual period.

Quality of Life Questionnaire

The SF-36 Questionnaire must be completed by the subjects prior to randomization and at specified follow-up visits according to Table 3.

Adverse Events (AEs)

Any untoward medical occurrence in a subject whether or not there is a relationship between the AE and the drug therapy administered will be documented and reported to the Sponsor as outlined in the Adverse Events Reporting Section (12.0) of this protocol.

Medication

All concomitant medication will be documented in the subject's chart and reported on the appropriate electronic case report form(s) (eCRF[s]). Any new medications or changes to existing medication will also be captured in the eCRFs. In case an AE is related to intake of drugs, details must be provided on the appropriate eCRF(s), including the AE form.

11.4.3 Unscheduled Visits

If a subject returns for visit outside of the protocol-defined visit windows provided in the Study Visits Section (11.4.1) of this protocol, the visit will be considered "unscheduled". If the unscheduled visit is for any purpose other than a repeat ablation procedure, an unscheduled visit CRF must be completed and the subject must also return for their next scheduled study visit. A list of the requested/recommended assessments that should be performed during the unscheduled visits is included in Table 3.0. If the unscheduled visit is for arrhythmia recurrence, the subject must be discontinued from the study as previously indicated in the Subject Disposition Section (9.6) of this protocol. All appropriate forms (eg, Final Status Form) must be completed for subjects that are discontinued due to arrhythmia recurrence within the Evaluation Period.

11.5 Core Laboratories for Evaluation Tests

A core laboratory will be used for the objective evaluation of Holter Monitor data. Initial evaluations will be performed by technical personnel trained in the evaluation of these tests, and will be reviewed by a cardiologist or an experienced EP technician. AF episodes will be evaluated per the definitions provided in this protocol.

12.0 Adverse Event Reporting and Documentation

Adverse event information will be collected throughout the study and will be recorded on the eCRFs by the study investigator or study coordinator per the reporting requirements outlined in table 8: AE Reporting Requirements below. Each AE must be reported regardless of classification, seriousness, intensity, outcome or causality. All AEs will be monitored until they are adequately resolved or explained in accordance with prevailing regulatory requirements.

